5.1 Study Duration

The planned clinical trial duration from the start of subject screening and enrollment to last subject out is anticipated to be from 12 to 24 months concurrent with FUEL-OLE. The final evaluation within the current study will be concurrent with the 12-month FUEL-OLE completion visit. Thus, each individual subject will be enrolled in the current study for only 12 months.

6.0 SELECTION AND DISPOSITION OF SUBJECTS

6.1 Number of Subjects

Subjects for this protocol will be recruited from the pool of patients in the FUEL Extension trial, from all participating centers that have the capacity to perform either ultrasound SWE or magnetic resonance elastography. We anticipate that we will have access to 100-200 subjects, although this will vary based on the start date for this study. If we achieve between a 50-75% consent rate, it would provide a sample size of 50-150 subjects.

6.2 Clinical Trial Population Characteristics

In order to be eligible for the clinical trial, subjects must fulfill the following criteria. Male and female subjects 12-19 years of age who meet all the Inclusion criteria and none of the Exclusion criteria will be enrolled.

6.3 Subject Inclusion Criteria

1. Enrollment in FUEL Extension Trial
2. Informed assent from subject, informed consent from parent/legal guardian as appropriate

6.4 Subject Exclusion Criteria

1. Non-enrollment in the FUEL Extension Trial
2. Subjects with contra-indications for MRI including presence of any indwelling, significant, ferromagnetic objects (including pacemakers and implantable cardiac defibrillators, or those unable to lie in the scanner without sedation (these subjects will be excluded from only the MRI components of this study)
3. Other exclusionary criteria will match those used for the FUEL Extension Trial

6.5 Subject Withdrawal Criteria

Subjects may voluntarily withdraw from the study at any time. In addition, the site principal investigators are free to withdraw a subject at any time for reasons of medical prudence. Any subject withdrawn from the FUEL Extension study will also be withdrawn from this ancillary study.

7.0 TREATMENT DESCRIPTION

7.1 Description of Treatment

All subjects participating in the present protocol will be participants in the FUEL-OLE protocol. Subjects in FUEL-OLE will be treated with udenafil for one year's time (87.5 mg twice daily). No additional treatment will occur in the present study.

7.2 Subject Identification Number

Each subject is assigned a subject identification number (SID). All interview and clinical research data are stripped of identifiers and labeled with the study number. The enrollment log with participant identifiers will be maintained at each site in a secured, locked location available only to the study staff. The informed consent form states that study data will be made available to the Data Coordinating Center (DCC) and NIH/NHLBI to ensure study safety and quality control. The subject's name and any other identifying information will not appear in any presentation or publication resulting from this study.

7.3 Method of Treatment Assignment and Blinding

Not applicable. This study is open label.

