5.0 STUDY DESIGN

This is an open-label extension study that integrates with the FUEL Extension Trial. FUEL-enrolled patients will have been randomized and double-blinded to either placebo or udenafil, and all patients entering the FUEL Extension trial will be placed on udenafil therapy. Therefore, approximately 50% of patients eligible to be enrolled in our study will be udenafil-naïve (U-) and 50% will have already completed 6-months of therapy (U+). As a part of FUEL-OLE, each participant will receive one year of udenafil treatment (87.5 mg twice daily). Both the U- cohort and the U+ cohort will have liver stiffness measured by ultrasound and MR elastography (where available), as described above. Thus, the U- subjects will have elastography measurements pre-udenafil and after 1 year of treatment. This will determine the impact of udenafil therapy on liver stiffness. Additionally, the U+ cohort from FUEL will allow us to determine if potential benefits of udenafil therapy are sustained over time by comparing measurements after 6 (baseline entry into our study) and 18 months of therapy (after 1-year of our study). The study visits are as follows:

1. Baseline visit: during the baseline visit, subjects will undergo ultrasound SWE and, if available at their center, magnetic resonance elastography. These will be coordinated with FUEL extension testing to ensure that the primary study is not interrupted. The additional blood work for this protocol will be obtained at the same time as the blood work for the FUEL extension study.
2. Follow-up visit: during the follow-up visit, subjects will undergo ultrasound SWE and, if available at their center, magnetic resonance elastography. These will be coordinated with FUEL extension testing to ensure that the primary study is not interrupted. The additional blood work for this protocol will be obtained at the same time as the blood work for the FUEL extension study.

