9.2 Sample Size Determination

Given the primary outcome is descriptive, sample size estimate is provided for secondary outcome 1 – evaluating the change in liver stiffness before and after udenafil treatment compared to a patient receiving on-going udenafil treatment. Elastography indices measured by US or MRI elastography from baseline to 12 months will be examined in both udenafil treatment groups (U+ and U-), using paired t-test or Wilcoxon signed- rank test, as appropriate. DiPaola et al. (17) demonstrated that liver stiffness measured by US-SWE significantly increased from baseline to 6-month post-TCPC (mean $1.18 \pm SD 0.29$ m/s to 2.08 ± 0.24 m/s, $p<.0001$).

Assuming a mean liver shear wave speed (SWS) of 2.08 with known SD 0.24 as our baseline liver stiffness, a total sample size of 24 subjects (12 per group) is required to achieve 85% power with alpha=0.05 to detect 10% reduction of liver stiffness (deemed clinically meaningful in an individual) at 12 months from baseline in the U- group. Assuming a maximal enrollment of 100 subjects, (approximately 50% of whom will be from the FUEL U- cohort), we would be powered to detect a difference of 3.75% reduction in liver stiffness.

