9.4.3 Secondary Outcomes

Secondary outcome 1

Baseline liver stiffness measured by ultrasound or MRI elastography will be compared between the two groups (U+ vs. U-) using appropriate statistics. Next we will assess change in liver stiffness from pre- to post-1 year udenafil treatment in the U-group as well as from 6 to 18 months of therapy in the U+ group.

Secondary outcome 2

Changes in liver stiffness, diastolic cardiac function (including E/E' and MPI), PAT measurement, and exercise measurements (including peak VO₂ and submaximal exercise measures) from baseline to 12 months will be quantified. Correlation between change in liver stiffness and changes in diastolic cardiac function and exercise measurements in the entire cohort and in the U- group and U+ group separately.

Secondary outcome 3

Bivariate analyses will examine 1) the correlation between each biomarker and liver stiffness measured by ultrasound and MRI elastography and 2) the correlation between change in each biomarker and change in liver stiffness from baseline to 12 months in both the U+ and U- cohorts.

The proteomic and transcriptomic data will be presented primarily as a descriptive report. Pairwise differences between groups may be sought using appropriate 2-group statistics, but we expect the limited sample size in this exploratory outcome to limit analysis to descriptive statistics.

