10.7 Study Limitations

While integrating with FUEL-OLE is a clear advantage and makes this FALD study feasible, the study will not have a placebo control arm. However, an active control (U+) should still allow assessment of how udenafil affects liver stiffness in a naïve patient. Each center may have access to only US SWE, MR elastography, or both. We expect most, if not all, centers to have access to US SWE, as it is now widely available, commonly employed in practice, and straightforward to use. Our (CCHMC) radiology core (including MRI physicist [name], and imaging post-processing laboratory) will be able to facilitate MR elastography capabilities at participating centers, ensuring the use of a standardized protocol across scanners. Experience in processing and analyzing/interpretation of this relatively new measurement technique should be mitigated by use of a radiology core. MR elastography is more difficult to add for currently non-capable centers, thus, MR elastography measurements will be limited to centers that have capabilities.

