11.0 REGULATORY/ADMINISTRATIVE PROCEDURES AND DOCUMENTATION

11.1 Data Collection

Data for each SWE and magnetic resonance elastography will be generated from each site and recorded on a case report form. This form will serve as the source document for each test and will be used to enter data into an electronic data capture (EDC) system (eCOS). US SWE data will be recorded from each site. MREL data will need to be sent anonymized to CCHMC for central processing/analysis.

The biomarker core lab will generate results for each blood specimen and will transmit that data electronically into the EDC system (eCOS). Subject identification will follow the same system as for the FUEL Extension trial. Each imaging study will be associated with the FUEL Extension identification number and each blood sample will be labeled with that same number.

FUEL-OLE enrollment takes place over a 2 day period. For clarity, often the initial FUEL-OLE day (called hereafter OLE-D1) and the final day of FUEL are the same visit. This visit consists of informed consent and assent, blood sample collection, EndoPAT testing, an echocardiogram, and exercise testing. Based on experience with the Udenafil study, this day takes 5-6 hours in total. Subjects will then return the next day (OLE-D2) for drug administration and 6-minute walk. Subjects will return at 12 months of FUEL-OLE for a final day repeating the above tests. FALD will ideally be integrated into this schedule with keen attention to preserving the integrity of the FUEL-OLE parent trial and preventing study fatigue as detailed below for each step. This plan was vetted and approved by the FUEL study subcommittee.

Subject recruitment: FALD will only be recruited by either the site PI or a study coordinator after a commitment is given to participate in FUEL-OLE. Recruiting should be done at the same time point as OLE to prevent unnecessarily repetitive patient contact.

Consent/Accent: Consent and assent for FALD will be obtained immediately following but only after consent/assent for FUEL-OLE has been obtained.

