Serum testing: Serum for the ancillary study will be obtained during the same venipuncture as used in FUEL-OLE. The serum sample will be processed, stored and shipped in parallel with the plasma sample that is being collected for the FUEL-OLE Trial. The processed serum (and the processed plasma for the FUEL-OLE protocol) will be shipped to the FALD core lab (University of Michigan) for testing. The ancillary study will require an additional 3 ml sample of blood (for a total of 6 ml).

Imaging: We have identified the morning of OLE-D2 as the optimal time for hepatic imaging.

[figure not shown]
Page 30 of 35

- US SWE: A complete US SWE exam lasts 5-10 minutes only. It is a portable test, and thus may be performed in either a radiology suite or any other clinical cardiology location used by the study. Additional limited anatomic imaging will also be obtained that takes approximately 1 minute.
- MRE: A complete MRE exam lasts approximately 15-20 minutes. Additional limited anatomic imaging will also be obtained that takes approximately 1 minute. Including patient travel to and from the MR scanner we anticipate an additional 20-40 minutes, making the total duration of MR testing 35-60 minutes.

All liver imaging should be able to be completed in 60-90 minutes.

- For initial FALD imaging, by starting OLE-D2 immediately with hepatic imaging at 7:30 or 8:00 AM, we would anticipate FUEL-OLE can begin its formal day's schedule with study drug administration by 9-9:30 AM. In total, we would expect OLE-D2 including hepatic imaging to still conclude by midday as anticipated by the FUEL-OLE protocol.
- For the OLE and FALD 12-month follow-up visit, we would again anticipate beginning the day for with hepatic imaging. To make this feasible, we can pay for hotel costs for those individuals enrolled in FALD at the 12-month visit so that the testing day may start early. Alternatively, imaging may be obtained at the end of the day following FUEL-OLE testing, although this is less ideal because exercise testing may influence FALD measures. Integration of same day testing should be feasible based on projected length of the testing day.

Imaging identifiers for these research studies will include only the site and subject study-specific ID. Following image obtainment at both time points, images from both US SWE and MRE will be sent to the imaging core. Images transferred will contain the site and subject identifiers and no protected health information.

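### Open-label treatment does not make masked image reading inapplicable: section 7.3 should require MR elastography pairs to be read masked to visit, and should say what protects the site-measured ultrasound values

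*Combined protocol and SAP*

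**What the plan says.** Section 7.3 covers treatment assignment and blinding in a single statement: "Not applicable. This study is open label". No other section masks an image reader or an ultrasound shear wave elastography (SWE) operator to visit.

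The drug effect is a before-after comparison. Section 5.0 states: "Thus, the U- subjects will have elastography measurements pre-udenafil and after 1 year of treatment", and then: "This will determine the impact of udenafil therapy on liver stiffness". Section 9.2 examines the 12-month change in each group "using paired t-test or Wilcoxon signed- rank test, as appropriate". Section 9.4.3 repeats the within-group approach ("Next we will assess change in liver stiffness from pre- to post-1 year udenafil treatment" for U-, and 6 to 18 months of therapy for U+) and names no test of the U- change against the U+ change. Section 10.7 concedes that there is no placebo arm and offers U+ as an active control.

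On reading, section 11.1 says "MREL data will need to be sent anonymized to CCHMC for central processing/analysis". SWE data are recorded at the sites, with the site form as source document. The same section also says that "images from both US SWE and MRE will be sent to the imaging core", identified by site and subject number. Section 10.7 relies on a radiology core to deal with limited "Experience in processing and analyzing/interpretation of this relatively new measurement technique". Section 9.3 places the unblinding of FUEL assignments at the completion of FUEL-OLE.

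**The concern.** At 12 months every subject is on udenafil, and section 4.3 predicts that stiffness will fall. Anyone who measures a scan knowing its visit knows which of the pair is expected to be lower. Expectation, or drift in reading practice over the year, could then move the follow-up values in one direction. A paired test within U- cannot separate such a shift from a drug effect.

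The privacy provisions do not settle this. Anonymizing a study removes the subject's identity. It does not remove the acquisition date or set the order of reading, and if scans are read as they arrive, arrival order alone reveals the visit. Central reading makes measurements more consistent between sites, but it does not by itself remove expectation or drift over time.

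The core that section 11.1 already describes could mask the MR reads. Because section 7.3 declares blinding inapplicable, the study manual and the later SAP have no prompt to add it.

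**Working it through.** **1. The plan's own figure.** Section 9.2 gives a baseline mean of 2.08 m/s, SD 0.24, a 10% reduction (0.208 m/s), 85% power and alpha 0.05. Taking 0.24 as the known SD of the change:

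n = [0.24 × (1.960 + 1.036) / 0.208]² = 11.95, so 12 per group, with power 85.1%.

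The stated 12 per group is reproduced. Two things follow. The calculation is for a single-group before-after change, which confirms where the inference rests. It also uses the baseline SD as the SD of change, which corresponds to a within-subject correlation of 0.5, because SD of change = 0.24 × √[2(1 − ρ)].

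**2. What a visit-related shift would do to that test.** Suppose the true change is zero and the follow-up reading is biased by a fraction b of 2.08. The paired t statistic then has noncentrality b × 2.08 × √n / SD of change. Section 6.1 expects 50 to 150 subjects and section 5.0 expects about half to be U-, so n = 25, 50 or 75. With SD of change 0.24:

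| Assumed shift | m/s | n = 25 | n = 50 | n = 75 |
|---|---|---|---|---|
| 0% | 0 | 5% | 5% | 5% |
| 2% | 0.0416 | 13.2% | 22.5% | 31.7% |
| 3% | 0.0624 | 23.9% | 43.7% | 60.4% |

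Entries are two-sided rejection rates at alpha 0.05. For n = 50 and a 2% shift, the noncentrality is 0.0416 × 7.071 / 0.24 = 1.226.

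**3. Range over the unstated correlation, n = 50.**

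| ρ | SD of change | 2% shift | 3% shift |
|---|---|---|---|
| 0 | 0.339 | 13.6% | 24.7% |
| 0.5 | 0.240 | 22.5% | 43.7% |
| 0.75 | 0.170 | 39.7% | 72.2% |

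The shifts of 2% and 3% are assumptions; nothing in the documents supports a particular value.

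**4. What these numbers can and cannot show.** The values 2.08 and 0.24 are SWE speeds, and SWE is measured at the sites. The tables show how sensitive the planned paired test is to a shift. They do not show how much masking at the core would recover, because the masked readings would be MR elastography. For MR the documents give no mean, SD or number of subjects; section 10.7 only limits it to capable centers.

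**5. Effect of the fix on the design.** Masked reading changes no sample size, power or alpha.

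**The case against.** The strongest reply is that the comparison is not wholly uncontrolled. Section 9.2 introduces secondary outcome 1 with ongoing-udenafil patients as the comparator, section 10.7 calls U+ an active control, and change is assessed in both groups. FUEL arm appears to stay masked until FUEL-OLE is complete, so a reader who knows the visit but not the arm should shift both groups alike, and the shift should show in U+. This stands as a partial check. It is not more, because the planned tests are within group and the U+ change also contains any continuing drug effect and the natural course of the disease. The check also depends on arm masking holding until measurements are final, which the protocol does not state.

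Second, section 7.3 correctly describes the treatment as open label, and no passage says that readers see the visit. That is fair: the gap is silence about reading, not a decision to unmask readers.

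Third, core masking does not reach the measure on which the sample size rests. SWE is expected at most or all centers and is taken by staff who will know the visit. This stands and limits what the fix can do.

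A reader might infer more: that the result on udenafil is already biased, that the rejection rates above are the trial's actual error rates, or that masking at the core would restore 5%. The documents support none of these. They contain no evidence of a shift, and the rates are in SWE units while the masking applies to MR.

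**Conclusion.** The point holds in a limited form. Section 7.3 sets blinding aside on the ground of open-label treatment, although the udenafil effect is judged by a within-group before-after change without placebo, and masked reading of MR elastography is feasible with the core already planned.

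The size of the bias is unknown. If a systematic SWE shift of 2-3% existed and the SD of change were 0.24 m/s, the false-positive rate of the U- test would be 13-32% (2%) or 24-60% (3%) for 25 to 75 subjects, with the range over other correlations shown above. These figures illustrate sensitivity; they do not estimate the benefit of masking.

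The finding concerns secondary aim 1. It might be read as a threat to the whole study, but the primary outcome is a description of stiffness and does not depend on the before-after comparison. The change should be made, because it improves the credibility of the only outcome for which the protocol gives a sample size calculation.

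**What to change.** Reword section 7.3, with a cross-reference in section 11.1, to say:

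- Treatment is open label; outcome assessment is masked as follows.
- The imaging core measures each subject's two MR elastography studies together, in random order, with visit label and acquisition date removed.
- Core readers and site SWE operators remain masked to former FUEL arm until reads are locked. This builds on the unblinding time in section 9.3, and it needs saying because paired reading moves the MR measurements closer to that time.
- SWE operators do not consult the baseline value when measuring at 12 months.
- The protocol states whether the site or the core SWE value is analysed, since section 11.1 records one at the site and also sends the images to the core.

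The SWE provisions limit operator bias at acquisition but do not remove it, and the limitations section should say so.

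Cost: no added scan, visit or subject. The documents give no cost for the core's work, so none can be claimed as negligible. The main downside is that MR measurements for analysis wait for the 12-month scan. Image-quality checks (section 11.2) and review for incidental findings (section 10.4) must therefore proceed separately when each scan is acquired. Section 10.5 already sends study results to treating physicians at study end, so later analysis reads fit that schedule.

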7.4 Sample Management

Sample collection and brain natriuretic peptide (BNP) testing will be performed during the collection of samples for the FUEL-OLE study. A plasma sample for BNP level will be obtained at the time of entry into the study and at the end of the 1-year open label extension trial. The samples will be collected and processed on-site and the plasma will be shipped on dry ice to the FUEL-OLE Central Laboratory located at the University of Michigan. The Central Laboratory will aliquot a portion of the sample for BNP testing in the University of Michigan Pathology Laboratory (UMPL) which performs this test for all patients seen in the University of Michigan Health System. In addition to this sample, FALD specific labs will be obtained at the same venipuncture. The samples that will be collected for those patients enrolled in the FUEL-OLE and the ancillary study are as follows:

Blood Samples

- 3 mL in a purple top (K2EDTA) PPT tube for BNP measurement (FUEL-OLE sample)
 - Invert the tube gently five times. Further inversion may cause alterations in sample integrity.
 - Centrifuge 10 minutes at 1600 x g using a refrigerated centrifuge (4°C)

- For each sample, the separated plasma will be transferred into two labeled polypropylene tubes (approximately 750 µL each), which will be stored at approximately -70°C within 2 hours of collection.
- 3.5 mL in a yellow top (SST) tube for serum isolation (Liver study sample)
 - Invert the tube gently five times. Further inversion may cause alterations in sample integrity.
 - Allow to clot for 30 min at room temperature
 - Centrifuge 15 minutes at 1600 x g using a refrigerated centrifuge (4°C)
 - For each sample, the separated serum will be transferred into two labeled polypropylene tubes (approximately 750 µL each), which will be stored at approximately -70°C within 2 hours of collection.

Biomarker Testing

- BNP testing will be performed by the UMPL
- NT-proBNP levels measurements will be performed on the residual plasma sample using a commercially available enzyme linked immunosorbent assay (ELISA) that will be run in the FUEL-OLE Central Laboratory.
- MicroRNA measures will be performed on the residual plasma sample in the FUEL-OLE Central Laboratory on total RNA isolated using miRNeasy total RNA preps (QIAGEN, Valencia, CA). miRNA qRT-PCR analysis will be performed using Taqman miRNA assays (Applied Biosystems, Foster City, CA). 5 ng total RNA will be used as an input into each reverse transcription reaction (RT) for each miRNA. Four replicates will be done for each miRNA, consisting of two replicate PCR reactions from each of the two replicate RT reactions, and the results were averaged. PCR reactions will be run on a 7500 Real Time PCR machine (Applied Biosystems) and analyzed using 7500 System SDS software (v1.4). For the candidate biomarkers, an equivalent number of anonymous, age-matched, healthy controls will be used for comparison. The control cohort will be derived from healthy individuals who present to the University of Michigan for elective surgical procedures.
- Enhanced Liver Fibrosis (ELF) score which is based on the serum levels of hyaluronic acid (HA), amino-terminal propeptide of type III collagen (PIIINP), and tissue inhibitor of metalloproteinase-1 (TIMP-1). Testing will be performed by the FUEL-OLE Central Laboratory using the serum sample. In accordance with prior studies, we will assign those patients with scores of <7.7 to the no or mild fibrosis group, 7-7-9.8 to the moderate fibrosis group, and >9.8 to the severe fibrosis group.

BNP testing will be performed by the UMPL, as described above. NT-proBNP levels measurements will be performed using a commercially available enzyme linked immunosorbent assay (ELISA) that will be run in the [name] laboratory. MicroRNA measures will be performed

in the [name] laboratory on total RNA isolated from plasma using miRNeasy total RNA preps (QIAGEN, Valencia, CA). miRNA qRT-PCR analysis will be performed using Taqman miRNA assays (Applied Biosystems, Foster City, CA). 5 ng total RNA will be used as an input into each reverse transcription reaction (RT) for each miRNA. Four replicates will be done for each miRNA, consisting of two replicate PCR reactions from each of the two replicate RT reactions, and the results were averaged. PCR reactions will be run on a 7500 Real Time PCR machine (Applied Biosystems) and analyzed using 7500 System SDS software (v1.4). For the candidate biomarkers, an equivalent number of anonymous, age-matched, healthy controls will be used for comparison. The control cohort will be derived from healthy individuals who present to the University of Michigan for elective surgical procedures.

Proteomic and transcriptomic analysis will take place using a multiplex Tandem Mass Tag (TMT) system allowing concurrent analysis of multiple samples. Plasma samples will be depleted of 14 high-abundant proteins using MARS14 (Agilent) or Seppro IgY14 (Sigma) columns. Depleted plasma samples (~50ug) will be alkylated and digested overnight. Samples will be labeled with the TMT Reagents per manufacturer's recommended protocol and mixed before sample fractionation (12 fractions). Each fraction will be analyzed by high-resolution, nano-LC-MS/MS using Orbitrap Fusion Tribrid mass spectrometer (ThermoFisher, Waltham, MA) to identify peptides/proteins and quantify reporter ion relative abundance. Data will be collected using the recently developed multinotch-MS3 method which improves the quantitation accuracy by minimizing the reporter ion ratio distortion resulting from fragmentation of co-isolated peptides (17). The data analysis will be performed using both commercial (Proteome Discoverer v 2.1) and publicly available software (e.g., MaxQuant). The performance and analysis of the proteomic profiling will be done in the Proteomics Resource Facility at the Department of Pathology, University of Michigan.

